## INTRODUCTION

Reduction of postoperative pain is a concern for all surgeons, as higher levels of pain are associated with decreased quality of life, prolonged convalescence, greater consumption of narcotic pain medications and prolonged length of stay.[1-3] Abdominal wall reconstruction often requires major midline laparotomies, myofascial releases and extensive dissection into the retromuscular, preperitoneal and retroperitoneal spaces, and therefore, not surprisingly, is associated with significant postoperative pain. In order to improve postoperative pain management and minimize opioid consumption and its associated side effects, multimodal approaches to postoperative analgesia have been used with increasing frequency in many fields of surgery[4] and are important components of protocols for enhanced recovery after surgery (ERAS). Such approaches have the objective of improving pain control using multiple classes of medications, ultimately minimizing opioid use [5]. One of the possible interventions of such multimodal approaches is the transversus abdominis plane block (TAP block), a regional anesthetic technique that blocks the neural afferents of the anterolateral abdominal wall.[4] Several studies have evaluated the utility of TAP blocks for postoperative analgesia after abdominal surgery and found a significant reduction in opioid consumption, pain scores and shortened length of stay.[6] Different local anesthetics can be injected to perform a TAP block, including lidocaine, bupivacaine hydrochloride, liposomal bupivacaine, and ropivacaine.[7] The utility of TAP blocks with bupivacaine hydrochloride in the management of acute postsurgical pain is limited by its short duration of action [8]. Exparel® (Pacira Pharmaceuticals, San Diego, California) is a bupivacaine liposomal injectable suspension marketed to diffuse over an extended 72 hour period. [9] The joint administration of Exparel® and bupivacaine hydrochloride has been shown in a placebo-controlled randomized controlled trial to reduce pain

immediately following open reduction internal fixation [10]. Fayeziadeh et al. suggested that Exparel® is efficacious in not only reducing acute narcotic requirements but also hospital length of stay following open abdominal wall reconstruction [4]. In addition, a Phase IV, prospective, single-center trial of 43 patients following ileostomy reversal surgery has suggested that despite its diffusion over only a 72-hour period, Exparel® may even be associated with decreased 30-day postsurgical opioid use [11]. The ability of Exparel® to produce extended relief is further supported by a multicenter study [12]. Despite the ability of both Exparel® and bupivacaine hydrochloride to reduce pain, the additional costs of Exparel® are irrefutable. Bupivacaine hydrochloride costs \$1.15 per 20 ccs of the product while Exparel® costs \$285 for the same amount [13].

We have incorporated the administration of Exparel® into an enhanced multifactorial recovery after surgery (ERAS) pathway designed to hasten patient recovery postoperatively [14]. A preliminary retrospective review of 30 patients undergoing our ERAS initiative revealed a mean hospital length of stay of 5.14 days [15], which is a reduction versus historical controls [16]. Although the efficacy of Exparel® has been assessed in a variety of studies with orthopedic, colorectal and gynecological surgery populations, high-quality scientific data evaluating Exparel® in the abdominal wall reconstruction literature is lacking. Furthermore, a recent Cochrane review [17] concluded that there is lack of data to support or refute the administration of Exparel® as a peripheral nerve block for postoperative analgesia since the current literature on Exparel® suffers a limited number of trials, with a small number of participants and inconsistency of results.

To determine if Exparel® influences on opioid requirements, postoperative pain levels, hospital length of stay and patient-reported quality of life following ventral hernia repair, we

propose a registry-based randomized clinical trial through the Americas Hernia Society Quality Collaborative (AHSQC). The AHSQC is a multicenter, nationwide quality improvement effort with the mission of improving the quality of hernia care [16]. We hypothesize that a TAP block with Exparel®, performed intraoperatively by a surgeon during open ventral hernia repair with mesh placed in retromuscular position, will result in decreased opioid requirements, reduced immediate and extended postoperative pain scores, shorten length of hospital stay, and improved quality of life when compared to a TAP block with Bupivacaine hydrochloride or placebo (normal saline), performed in the same manner and in the same population.

The aims of this study are:

Specific Aim #1: To determine if intra-hospital opioid requirements over initial 72 hours differ following the administration of Exparel®, Bupivacaine hydrochloride, or placebo (normal saline) through a TAP block during open ventral hernia repair with retromuscular mesh placement.

Opioid consumption will be assessed by measuring the cumulative dose of opioids administered through intravenous and oral preparations. Intravenous opioids will include all opioids infused through a patient-controlled analgesia device (PCA) and intravenously as a rescue medication for breakthrough pain. Specific time points for assessments are: at post-anesthesia care unit (PACU/POD0), and daily during the hospital stay up to a maximum of 7 days. Opioid requirements will be recorded and converted into morphine equivalents for standardization. In addition, we aim to record and analyze: (1) amount of opioids administered intraoperatively by the anesthesiologist, (2) cumulative dose of opioids during the first 7 days of hospital stay and (3) time to first oral opioid use.

Specific Aim #2: To determine if immediate and extended pain scores differ following the administration of Exparel®, Bupivacaine hydrochloride, or placebo (normal saline) through a

TAP block during open ventral hernia repair with retromuscular mesh placement. Immediate time points include while patients are at PACU/POD0, and daily during the hospital stay up to a maximum of 7 days. An extended time point includes 30-days postoperatively.

Specific Aim #3: To determine if hospital length of stay differs following the administration of Exparel®, Bupivacaine hydrochloride, or placebo (normal saline) through a TAP block during open ventral hernia repair with retromuscular mesh placement.

Specific Aim #4: To determine if 30-day patient-reported quality of life (PRQOL) scores differ following the administration of Exparel®, Bupivacaine hydrochloride, or placebo (normal saline) through a TAP block during open ventral hernia repair with retromuscular mesh placement.

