## OUTCOMES OF INTEREST

### **Primary outcomes of Interest**

Primary outcomes of interest are opioid requirements and pain scores over initial 72 hours of the postoperative period. Opioid requirements will be assessed by measuring the cumulative dose of opioids administered intravenously (infused through a patient-controlled analgesia device as well as the quantity of opioids administered intravenously as rescue, if needed) and the quantity of opioids administered through oral preparations. This will be assessed at time points: at day of surgery (while patients are at PACU or the nursing floor), at postoperative days 1, 2 and 3. Additional time points include daily assessments during the rest of the hospital stay up to a maximum of 7 days. The total dose of opioids used at each time point will be recorded and converted into morphine equivalents for standardization and analysis. We will record the cumulative dose of opioids from 0 hours to 72 hours after the operation and for the total hospital length of stay (up to a maximum of 7 days). In addition, we aim to record the dose of opioids administered intra-operatively by the anesthesiologist, time for first oral opioid dose over the first 72 hours (discontinuation of PCA), and the percentage of patients not requiring opioids over the first 72 hours.

Pain scores will be determined using a 100mm visual analog scale (VAS). The VAS is a 100mm horizontal line with two endpoints: 0 (no pain) and 100 (worst imaginable pain). While in the hospital, subjects are to assess, “How much pain are you experiencing right now?” Pain scores will be assessed at baseline during preoperative evaluation, at day of surgery (PACU or nursing floor), at postoperative days 1, 2 and 3. Additional time points include daily assessments during the rest of the hospital stay up to a maximum of 7 days.

Additional pain scores will be obtained using the Patient-Reported Outcome Measurement Information System (PROMIS) Pain Intensity 3a survey, which is part of the

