**Randomization**

Patients will be randomized using a computer-generated random allocation sequence, by the investigational pharmacy personnel. The random allocation sequence will be implemented with REDCap®, where a randomization allocation table will be generated and uploaded into REDCap® by the study statistician listed in this protocol. Randomization will occur during the operation at the end of adhesiolysis, and at the beginning of abdominal wall reconstruction, to allow for sufficient time for the investigational pharmacy to prepare and dispense the assigned intervention. This study will be double-blinded since patients will be blinded to their assigned intervention until their participation in the study is complete, and also surgeons will be blinded to the intervention assigned to the subject. Only the investigational pharmacy will be aware of the

assigned intervention and this information will be stored in the appropriate randomization platform in REDCap. The study coordinator and other research personnel who will be abstracting opioids doses and pain scores from patients will also be blinded to the intervention that was assigned to patients.

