### **Surgical Procedure**

All patients will undergo the same operation, under a standard of care protocol. Our surgical approach to open ventral hernia repair with retromuscular mesh placement is further detailed. Skin preparation, hair removal, perioperative antibiotics and venous thromboembolism prophylaxis will be performed per Surgical Care Improvement Project protocol guidelines. The procedure will be performed through a midline incision. Upon entering the abdominal cavity, all adhesions between intra-abdominal contents and the anterior abdominal wall are routinely lysed using sharp dissection. When present, hernia contents are reduced back to the cavity. At the end of adhesiolysis, the surgeon will ask the OR nurse to contact the investigational pharmacy via telephone, who will randomize the subject. The investigational pharmacy will be responsible for preparing and dispensing the assigned intervention. The OR nurse will receive the drug from the investigational pharmacy in a standardized bag and will dispense it to the surgeon at the time of the TAP block. Neither the surgeon nor other members of the surgical team will be informed about which of the interventions were assigned to the specific patient. Electronic medical records will contain the information: "Patient was randomized and assigned to receive intervention according to randomization performed by investigational pharmacy."

Retromuscular hernia repair is performed initially incising the posterior rectus sheath just lateral to the linea alba. The release will be performed at least 5 cm above and below the fascial

defect, and retrorectus dissection is carried out laterally in the direction of the linea semilunaris.

If deemed necessary, a posterior component separation will be performed by incising the posterior lamella of the internal oblique, dividing the fibers of the transversus abdominis muscle and dissecting the preperitoneal and retroperitoneal spaces of the lateral abdominal wall laterally.

At the end of the myofascial release, the assigned intervention drug will be dispensed in syringes to the surgeon who will perform the perform a TAP block under direct visualization.

*The TAP block*

Injections of the designated drug (group 1, 2 or 3) will be performed under direct visualization by the attending surgeon, in 5 vertical levels, to the thoracoabdominal nerves (from T7 to T11).

Other details relating to administration will be per manufacturer's instructions (4).

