The posterior sheath will be reapproximated, and a standard piece of polypropylene mesh will be placed in the retromuscular space.

Mesh type will be defined by the surgeon intraoperatively according to the patient and hernia-specific variables. Mesh fixation will be performed circumferentially using mechanical sutures. Closed suction drains will be placed above the mesh and in the subcutaneous space, and the timing of removal will be based on the surgeon's standard practice. Fascial closure and management of wound dressings will also follow the surgeon's standard practice.

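### The intraoperative opioid measure counts doses given before the TAP block; split it at the recorded block time

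*Combined protocol and SAP*

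**What the plan says.** The relevant text is in four places in the combined protocol and SAP.

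- **INTRODUCTION, Specific Aim #1.** The aim concerns opioid requirements after the study product has been injected. It then adds: "In addition, we aim to record and analyze: (1) amount of opioids administered intraoperatively by the anesthesiologist". Primary outcomes of Interest repeats the item: "we aim to record the dose of opioids administered intra-operatively by the anesthesiologist". Neither place divides the dose at randomization or at the block.
- **Randomization.** "Randomization will occur during the operation at the end of adhesiolysis, and at the beginning of abdominal wall reconstruction".
- **Surgical Procedure.** The block follows the retrorectus dissection and any component separation: "At the end of the myofascial release, the assigned intervention drug will be dispensed in syringes to the surgeon". The operation then continues: "The posterior sheath will be reapproximated, and a standard piece of polypropylene mesh will be placed in the retromuscular space". Mesh fixation, drains and fascial closure come after that.
- **Primary outcomes of Interest.** "Primary outcomes of interest are opioid requirements and pain scores over initial 72 hours of the postoperative period". The opioid total is built from PCA, intravenous rescue and oral doses, and the clock is stated: "We will record the cumulative dose of opioids from 0 hours to 72 hours after the operation". Its time points are "at day of surgery (while patients are at PACU or the nursing floor), at postoperative days 1, 2 and 3".

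No section requires the time of the block to be recorded.

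**The concern.** An outcome should cover a period in which the treatment can act. The intraoperative dose covers the whole operation, and treatment begins part-way through it. Opioid given during incision and adhesiolysis precedes even the allocation. Opioid given during the myofascial release follows allocation but still precedes the injection. Neither can respond to the product injected.

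As written, the intraoperative comparison is therefore hard to interpret. A null result could mean that the block does nothing during the rest of the operation, or that most of the dose was given before the block. The figure recorded cannot separate the two. Opioid given after the block but before the operation ends is post-treatment, yet it appears only inside the undivided figure because the 0-72 h total starts after the operation. If the block time is not noted at surgery, it may not be possible to make the split later.

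**Working it through.** **Order of events.** Set side by side, the sections give this sequence:

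| Period | Treatment status | Where the opioid is counted |
|---|---|---|
| Start of operation to end of adhesiolysis | Before randomization | Intraoperative dose |
| Randomization to end of myofascial release | Randomized, not yet treated | Intraoperative dose |
| Block to end of operation | Treated | Intraoperative dose only |
| 0-72 h after the operation | Treated | Primary opioid total |

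The first three rows are pooled into one number. Only the third can show an effect of treatment.

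**Dilution.** The plan gives no figure for the intraoperative dose, so there is none to reproduce. Let f be the share of the mean intraoperative dose given before the block, and d the relative effect on the part given after it.

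Visible effect = d × (1 − f)

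Neither f nor d is in the documents. For illustration I take d = 30%. Power Calculation hypothesizes that reduction for total opioid consumption over the hospital stay, not for doses late in surgery, so using it here is an assumption. Results over a wide range of f:

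- f = 0.25: 0.30 × 0.75 = 22.5%
- f = 0.50: 0.30 × 0.50 = 15%
- f = 0.75: 0.30 × 0.25 = 7.5%
- f = 0.90: 0.30 × 0.10 = 3%

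**What this could mean for power.** Power Calculation gives 49 per arm, alpha 0.05 and 80% power, but no SD. Solving the two-sample normal formula for the implied coefficient of variation (two-sided) gives CV = 0.30 / [(1.960 + 0.842) × √(2/49)] = 0.53. If the whole intraoperative dose had that same CV (a further assumption), power = Φ(visible effect / (0.53 × √(2/49)) − 1.96). This gives 56% at f = 0.25, 29% at f = 0.50 and 10% at f = 0.75. These values show direction only. The post-block dose may have a larger relative spread than the whole dose, so splitting does not guarantee a matching gain in power. What it does secure is a measure that can be interpreted.

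**Reach into the primary total.** The time from block to end of operation is not given. If it is h hours, a window of 0-72 h after the operation leaves out h/(72 + h) of the hours since the block:

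- h = 0.5: 0.7%
- h = 1: 1.4%
- h = 2: 2.7%
- h = 3: 4.0%

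Now suppose the omitted doses are a share g of all post-block opioid, and the relative effect on them is r, anywhere from 0 to 60%. Including them changes a 30% effect to (1 − g) × 0.30 + g × r:

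- g = 1%: 29.7% to 30.3%, power 79% to 81%
- g = 5%: 28.5% to 31.5%, power 76% to 84%
- g = 10%: 27% to 33%, power 71% to 87%

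All of these inputs are assumed, with CV held at 0.53. The primary total moves little unless g is large.

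**The case against.** The strongest reply is that the trial asks about postoperative analgesia, and its primary total is defined to match. PCA boluses and rescue doses are driven by the patient, whereas intraoperative doses are given by the anesthesiologist. Keeping the two apart is coherent. The intraoperative dose is introduced as an addition and is not the powered endpoint. All of this stands, and it limits the weight of the point.

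Four stronger readings are tempting, and the documents support none of them.

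- *The primary clock is wrong because it starts after the operation.* A purely postoperative 72 h total is a legitimate choice. It starts at the same surgical event in every arm.
- *Pre-block dosing biases the comparison.* Doses before randomization are balanced in expectation. Between randomization and the block, only the investigational pharmacy knows the allocation. A chance difference is ordinary sampling error, which the test level already covers.
- *Pre-treatment opioid enters the powered endpoint.* Power Calculation refers to total opioid over the stay without mentioning intraoperative doses. Primary outcomes of Interest, however, builds the total from PCA, rescue and oral opioid and lists the intraoperative dose separately.
- *The pre-block dose must be a covariate.* Statistical Analysis plans Mann-Whitney U tests for opioid requirements, which take no covariate. Adjustment would need another model. It may improve precision but corrects no error.

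The reply leaves one thing unanswered: the intraoperative dose is to be analysed under an aim about what follows the injection, and part of it comes before the injection.

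**Conclusion.** The point holds for the intraoperative opioid measure only. The order of events is explicit in the protocol, so no assumption is needed to conclude that any opioid given before the block is counted in an outcome it cannot inform. The size of the dilution is unknown because the pre-block share is not given. The illustrative range of 22.5% down to 3% rests on an assumed share of 0.25 to 0.90 and on a 30% effect borrowed from a different total.

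The primary 0-72 h comparison is not biased and needs no redefinition. This is a cheap improvement to an additional measure and does not threaten the trial's main conclusion.

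**What to change.** 1. In Surgical Procedure, require the clock time of the TAP injection to be recorded.
2. In Specific Aim #1 and Primary outcomes of Interest, define the intraoperative opioid outcome as the dose given after the block and before the operation ends.
3. Report the pre-block dose by arm as a descriptive baseline variable, not as an outcome. Using it as a covariate is optional; if wanted, Statistical Analysis must name a model that allows it.
4. Keep the postoperative 0-72 h total as the primary opioid measure. Add a sensitivity analysis of opioid from the block to the same 72 h end point, so that only the starting point differs.

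The cost is one timestamp per patient, slightly more abstraction to divide the intraoperative doses at that time, and a few lines of wording. Treatment, sample size and the primary analysis do not change.

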## STUDY DESIGN

As in previous randomized controlled trials executed by our research group, the AHSQC will serve as a platform for data collection. Additional data not captured by the AHSQC will be recorded by a trained study coordinator or research fellow and uploaded into Research Electronic Data Capture ( RedCAP®). Baseline and intraoperative variables, as well as some of our outcomes of interest (30-day pain scores, hospital length of stay, PRQOL), are already captured within the AHSQC database, allowing for follow-up and data capture with minimal additional effort outside that of routine care (11).

This will be a double-blind, 3-arm, randomized controlled trial with a treatment 1: treatment 2: control allocation ratio of 1:1:1. No important changes to the methods after trial commencement are anticipated. We anticipate that this will be a single-institutional study of patients undergoing elective open ventral hernia repair at Cleveland Clinic Comprehensive

Hernia Center ( Main Campus, Cleveland Clinic Foundation, Cleveland, Ohio, USA) performed by 4 staff surgeons: [name] (PI), [name] (co-I), [name] (co-I) and [name] (co-I). Nonetheless, we do not discard to turn this trial into a multi-institutional trial in the future. No important changes to the methods after trial commencement are anticipated. No interim analyses will be performed, and no stopping guidelines are needed since the interventional arms of this study are already currently performed at our institution, and we do not anticipate adverse events requiring study suspension.

Inclusion criteria are all adult patients (at least 18 years of age) undergoing open, elective, clean or clean-contaminated (wound classification), ventral hernia repairs with mesh placed in retromuscular position. We have no restrictions on hernia size, and the indication of the operation will be at the discretion of the attending surgeon. Exclusion criteria include: (1) patients unable to give informed consent, (2) patients with allergy, hypersensitivity or contraindication to bupivacaine, (3) patients with history of chronic liver disease with moderate or severe impairment in liver function defined as a Child-Pugh class B or C (4) patients with a history of chronic renal insufficiency on dialysis; (5) patients who are considered chronic opioid users, defined as daily or near daily use of opioids for at least 90 days in the past year and (6) patients from vulnerable populations as further detailed in this protocol. Patients scheduled for minimally invasive hernia repairs or open ventral hernia repairs with mesh placed in a position other than retromuscular will also be considered exclusion criteria. Also, open repairs performed through a different incision than the standard midline approach will also be considered exclusion criteria.

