### **Additional Outcomes of interest**

Pertinent baseline patient demographics, hernia variables, intraoperative details and 30-day outcomes including surgical and medical complications are also captured routinely for all patients in the AHSQC, as a standard of care.

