## STATISTICAL ANALYSIS

Statistical analysis will be performed by the DDSI statistician listed in this protocol, who will determine the appropriate statistical tests for each outcome of interest. Categorical variables will be reported using proportions and analyzed using Pearson's Chi-square. Continuous variables will be reported using median and interquartile range due to their non-parametric nature and examined using either a Student's t-test or a Wilcoxon signed rank test. Pain scores,

opioid requirements, hospital length of stay, and PRQOL requirements will be compared using Mann-Whitney U tests.

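### Surgical extent varies by design and the protocol ties it to pain, but neither allocation nor the primary comparison uses it: precision is given up and chance imbalance goes uncorrected

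*Combined protocol and SAP*

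**What the plan says.** - **Eligibility (Study Design).** The trial takes adults "undergoing open, elective, clean or clean-contaminated (wound classification), ventral hernia repairs with mesh placed in retromuscular position". On size it adds: "We have no restrictions on hernia size, and the indication of the operation will be at the discretion of the attending surgeon".
- **Operation (Surgical Procedure).** The section opens with "All patients will undergo the same operation, under a standard of care protocol". Further on it makes the lateral release conditional: "If deemed necessary, a posterior component separation will be performed by incising the posterior lamella of the internal oblique".
- **Source of pain (Introduction).** The protocol attributes the marked pain of abdominal wall reconstruction to the long midline incision, the muscle releases and the wide dissection.
- **Allocation (Randomization).** "Patients will be randomized using a computer-generated random allocation sequence, by the investigational pharmacy personnel", in a 1:1:1 ratio. No stratification factor, blocking or minimisation is described. On timing: "Randomization will occur during the operation at the end of adhesiolysis".
- **Data (Additional Outcomes of interest).** The registry already holds "Pertinent baseline patient demographics, hernia variables, intraoperative details and 30-day outcomes".
- **Analysis (Statistical Analysis).** Together with pain scores, "opioid requirements, hospital length of stay, and PRQOL requirements will be compared using Mann-Whitney U tests". The statistician is to choose the tests, but no covariate or adjusted model is named.

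**The concern.** Small retrorectus repairs and wide repairs with lateral release enter one comparison. By the protocol's own account, the amount of dissection contributes to the pain that drives both primary outcomes. Some of the spread in opioid dose and pain score is therefore probably predictable from facts known before the drug is assigned. A Mann-Whitney test takes no covariates, so all of that spread counts as noise.

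Two things are at stake. The first is power: the sample size targets only 80%, for one contrast, and shows no SD to suggest a margin. The second is how the realised result will read. If the arms differ visibly in hernia width, the plan offers no prespecified correction. Any adjustment chosen at that point would look data-driven, all the more because the choice of tests is left open.

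**Working it through.** **Inputs from the protocol.** Power Calculation: 30% reduction in opioid use (Exparel against placebo), alpha 0.05, power 80%, 49 per arm, 10% dropout, 54 per arm, 162 in total. Two-sided testing is assumed because sidedness is not stated.

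**Inputs not in the protocol.** The SD and control mean of opioid dose, the share of outcome variance (R²) explained by hernia width and wound class, and the wound-class split. R² is varied over 0.10 to 0.30, and the prevalence of a binary factor over 20% to 50%.

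**1. The plan's own figure.** 49 × 1.10 = 53.9, rounded to 54, and 3 × 54 = 162; both agree. The 49 cannot be rebuilt without an SD. Solving backwards, d = (1.960 + 0.842) × √(2/49) = 0.566, so the SD is 0.30/0.566 = 0.53 of the control mean.

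**2. Gain from adjustment (linear-model approximation).** The residual SD shrinks by √(1 − R²), so power = Φ(2.802/√(1 − R²) − 1.960). The number per arm for 80% power is about 49 × (1 − R²), rounded up.

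| Assumed R² | √(1 − R²) | Power at 49 per arm | n per arm for 80% |
|---|---|---|---|
| 0.10 | 0.949 | 84% | 45 |
| 0.20 | 0.894 | 88% | 40 |
| 0.30 | 0.837 | 92% | 35 |

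**3. Check by simulation** (49 per arm, d = 0.566, normal outcomes, 4,000 trials per setting). Mann-Whitney power stays near 78% whatever the R². Covariate-adjusted linear regression reaches 83%, 87% and 92% at R² of 0.10, 0.20 and 0.30. With no true effect, both reject about 5% of the time (4.7% to 5.7%).

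**4. Chance imbalance at 54 per arm.** The standardised difference in a covariate between two arms has SD √(2/54) = 0.192.
- More than 0.2 SD: 30% for a given pair, 55% for at least one of the three pairs.
- More than 0.3 SD: 12% and 26%.
- Binary factor, gap of at least 10 percentage points in a given pair: 18% at 20% prevalence, 25% at 30%, 29% at 50%.

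**5. What an imbalance does to the estimate.** The shift is √R² × imbalance, in outcome SDs. For 0.2 SD it is 0.063, 0.089 and 0.110 at R² of 0.10, 0.20 and 0.30, or 11%, 16% and 19% of 0.566. For 0.3 SD at R² = 0.20 it is 0.447 × 0.3 = 0.134, or 24% of 0.566.

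**6. Limit of step 2.** The √(1 − R²) factor belongs to a linear model. In a proportional-odds model, adjustment does not shrink the standard error of the log odds ratio. Power rises because the adjusted log odds ratio moves further from zero. The percentages are therefore a guide to the gain, not an exact figure for that model.

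**The case against.** The strongest reply is that nothing in the plan is invalid. Randomisation protects the unadjusted test, and its 5% error rate already allows for chance imbalance. This stands. A reader might infer that mixing hernia sizes biases the comparison or inflates false positives; step 3 shows that it does not. Nor is broad eligibility itself an error. Elective surgery, midline incision, retromuscular mesh and the exclusion of chronic opioid users already narrow the population.

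Other stronger readings also fail:
- *Imbalance is likely.* For a given pair, more than 0.2 SD occurs 30% of the time. The 55% is for any of three pairs, and the 29% for a binary factor needs 50% prevalence, which the documents do not give.
- *Every interval is widened.* Statistical Analysis plans medians, interquartile ranges and tests, but no confidence intervals.
- *Clean-contaminated patients eat later and so receive acetaminophen and gabapentin later.* Multimodal Pain Management ties those drugs to oral intake, but nothing links oral intake to wound class.
- *The protocol contradicts itself about the operation.* The opening sentence of Surgical Procedure is loose, but the optional release is disclosed in the same section.

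Two further points stand in part. The gain rests wholly on an assumed R², and wound class is not among the sources of pain that the Introduction names. Also, muscle release, which it does name, is decided after allocation, so width serves as its pre-allocation proxy. Neither removes the case: a weak covariate brings a small gain at a small cost.

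**Conclusion.** The concern holds as one of efficiency and of uncorrected chance imbalance in the realised trial. The trial is valid without the change.

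At an assumed R² of 0.10, 0.20 or 0.30, adjustment would raise 80% power to about 84%, 88% or 92%. A given pair of arms differs by more than 0.2 SD in a covariate 30% of the time, which shifts the estimate by 11% to 19% of the effect implied by 49 per arm over the same range of R². These figures rest on the assumed R², two-sided testing, the back-solved effect of 0.566 SD and a linear approximation. The documents give no figure for the prognostic strength of hernia width or wound class.

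**What to change.** In Statistical Analysis, prespecify one primary model for each of 72-hour morphine equivalents, 72-hour pain scores and length of stay: a proportional-odds model with arm, hernia width (continuous) and wound class (clean or clean-contaminated). It accommodates skew and zero doses. Zeros must be expected, since the primary-outcome section plans to report the share of patients who need no opioid in the first 72 hours. A log-dose model would fail on those zeros and is not rank-based.

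- Use registry values determined before allocation, and say so. Allocation follows adhesiolysis, so width and wound class should be known by then. That is an inference: the protocol does not say when either is recorded, and the registry description names neither explicitly.
- Keep Mann-Whitney as a sensitivity analysis.
- Show component separation descriptively by arm, because it is decided after randomisation.

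Stratifying the allocation table by wound class and rewording the opening of Surgical Procedure are optional; the gain does not depend on either.

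The cost is analysis-plan wording, a little code and confirmation of when the two covariates are recorded. The downside is that a model-based odds ratio, conditional on the covariates and resting on proportional odds, replaces a simple rank test.
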